3.1.3 DATA SAFETY MONITORING BOARD (DSMB)

Blinded safety data will be reviewed by the sponsor on an ongoing basis throughout the study period. In addition, an independent group of experts (DSMB) will have a

safety oversight responsibility and will advise STALICLA. The DSMB shares with STALICLA the responsibility for regularly monitoring the overall safety of the patients in the trial by carefully reviewing overall rates of AEs including SAEs and other specified safety events. The DSMB will help STALICLA to minimize patient exposure to unnecessary risk.

The primary responsibilities of the DSMB are to 1) review and evaluate the accumulated study data for patient safety, study conduct and progress, and 2) make recommendations to STALICLA concerning the continuation, modification, or termination of the trial. The DSMB will consider study-specific data as well as relevant background knowledge about the disease, STP1, and patient population under study.

The DSMB recommendation should focus on safety data. There is extensive experience and available data with the use of [REDACTED] ([REDACTED]) and of [REDACTED] (in the U.S.) alone for other indications and the AE profile of both individual drugs is known. The DSMB should take into consideration this clinical experience to evaluate overall rates of AEs reported for this study. Should the DSMB consider that the combination of [REDACTED] ([REDACTED] mg twice a day) and [REDACTED] ([REDACTED] mg twice a day) is safe for the study population, they should recommend continuing the study according to the protocol.

The DSMB consist of a minimum of 3 and up to 4 STALICLA-independent members. They will be independent from the study. The board will consist of:

- 2 MDs specialized in ASD/neuro-immunology/neurodevelopmental disorders (NDDs).
- One MD or PhD with extensive experience in drug development in ASD or neurodevelopmental disorders, and
- Optionally 1 Clinical Pharmacologist.

Once the first dose cohort (i.e., 8 patients) has finished the 2 weeks of treatment and the 2 weeks of follow-up, the DSMB will initially review and evaluate the blinded study data but has the right to request individual unblinded data when justified. The blinded study data will include:

- Interim/cumulative data for evidence of study drug-related AEs:
- Interim/cumulative safety laboratory data with a more specific evaluation of potential electrolyte imbalance as described in the study protocol and coagulation parameters.
- ECG and vital signs data (including orthostatic blood pressure changes).
- Data quality, completeness and timeliness.
- Adherence to the protocol.

The DSMB will specifically assess the changes from baseline all safety laboratory data with a more specific evaluation of potential electrolyte imbalance and coagulation parameters.

The DSMB will provide recommendations to STALICLA as to whether the study should continue according to the protocol (i.e., proceeding with the recruitment for the second dose level of [REDACTED] mg twice a day (6 hours apart) of [REDACTED] mg twice a day (6 hours apart) of [REDACTED]) or be terminated.

3.1.4 END OF STUDY

The end of the study is defined as the date when the last patient, last observation (LPLO) occurs. LPLO is expected to occur approximately 4 weeks after enrolment of the last patient.

3.2 RATIONALE FOR STUDY DESIGN

There is currently no data on the safety and PK of [REDACTED] given in combination. Therefore, the present study evaluates safety and tolerability as the primary outcome, using doses which are used clinically, with the goal of confirming the good safety and PK profiles of the combination in this study population. This is a parallel-group, multiple dose study whereby the dose of [REDACTED] will only be increased if the safety/tolerability results support the start of the second dose level as evaluated by an independent DSMB. The use of a placebo-controlled arm allows for a fair comparison to assess safety and potential PD effect of STP1. Potential clinical improvement of the patients will be explored and may help identify the endpoints most sensitive to change. The outcomes will be used to design a larger dedicated Phase 2 trial in adults and adolescents.

3.2.1 RATIONALE FOR DOSAGE SELECTION AND TREATMENT DURATION

As [REDACTED] is expected to be the main driver of the STP1 effect, only the dose of [REDACTED] will be increased between the two cohorts while the dose of [REDACTED] will be fixed to [REDACTED] twice a day (6 hours apart).

The starting dose of [REDACTED] mg of [REDACTED] twice a day (6 hours apart) was chosen based on the PK and safety data available from the literature. The margins of safety (MOS) associated with the starting dose is [REDACTED] and was derived from the preclinical toxicokinetic data and the estimated NOAEL in the toxicology studies performed in the dog, the most sensitive species to STP1. The second dose level of [REDACTED] mg twice a day (6 hours apart) is expected to allow [REDACTED] to reach a C_{trough} of approximately 13 ng/mL, corresponding to 56 nmol which is within the range of PDE4 IC₅₀ [Huang et al, 2006]. Hence, the 5 and 10 mg twice a day (6 hours apart) doses are expected to modulate PDE4 and might already show positive PD effects (e.g., on EEG endpoints or on processing speed, as assessed by a computerized cognitive battery). The safety / tolerability profile should remain acceptable as per extensive data collected in [REDACTED] and from clinical trials and summarized in Table 1, with nausea as the most frequent AE reported with doses of 30 mg/day. In this study, the maximum dose planned is 20 mg/day for 2 weeks.

[REDACTED] alone given to children and adolescents with ASD, aged 2 to 18 years, has been shown to improve core symptoms in a subset of patients with an acceptable risk/benefit ratio at a dose of 1 mg twice a day (6 hours apart) for 3 months [Lemonnier et al, 2017].

The [REDACTED] steady state concentration should be achieved after 4 days of treatment. Hence, a 2-week treatment duration with STP1 was considered appropriate to provide sufficient safety, tolerability and PK information for both [REDACTED], after multiple dosing of STP1. Beneficial impacts of PDE4 inhibitors on cognition, and more specifically processing speed, have been recently described in different studies involving healthy volunteers [Chiu et al, 2014; Heckman et al, 2018; Van Duinen et al, 2018]. Two weeks of treatment are thought to be sufficient to observe potential PD

effects on EEG recordings, or cognition and processing speed (as assessed by the [REDACTED] or KiTAP test battery).

3.2.2 RATIONALE FOR STUDY POPULATION

Adult male or female individuals with idiopathic ASD and meeting the 2 primary criteria for ASD-Phen1 will be enrolled in this study.

Since this is the first time that STP1 will be tested in humans, only adult patients with ASD-Phen1 will be included in the study. In addition, no prospect of direct clinical benefit of STP1 has been demonstrated yet and a treatment duration of 2 weeks will not allow for a potential impact on functional outcomes.

STP1 is specifically designed to alleviate the cellular and molecular perturbations identified in patients with ASD-Phen1; therefore, only individuals with idiopathic ASD matching the 2 ASD-Phen1 primary criteria will be enrolled in this trial. This subpopulation is defined by 1) [REDACTED]

nd 2)

[REDACTED]. Identifying the right subpopulation is critical not only to increase the chance to respond to STP1 but also to avoid enrolling patients with ASD for whom STP1 may worsen their symptoms. In fact, another subpopulation of patients with ASD showed improvement in their symptoms when presenting with fever [Grzadzinski et al, 2018].

3.2.3 RATIONALE FOR PHARMACOKINETIC SAMPLING

Blood PK samples will be collected from all patients for measurement of plasma and urine concentration of [REDACTED]. These STP1 PK data will be used to evaluate potential correlation between blood exposure and AE incidence, will be compared with PK data [REDACTED] described in the literature, and will be used to explore the potential impact of [REDACTED] (potent diuretic) on the PK and excretion of [REDACTED]. Combined with the safety, tolerability and PD data collected, these data will help identify the dose levels to be used in a subsequent Phase 2 trial.

3.2.4 RATIONALE FOR BIOMARKER ASSESSMENTS

- Electroencephalographic (EEG) recordings

Gamma band activity has established neural mechanisms, which include the local circuit glutamate/GABA interactions [Cardin et al, 2009; Lally et al, 2014]. During sensory processing, for instance, gamma is associated with bottom-up sensory processing of basic stimulus properties [Brosch et al, 2002]. In addition, enhancing effects of the PDE4 inhibitor roflumilast on sensory gating in healthy volunteers were recorded using an Event Related Potential (ERP) paradigm [Heckman et al, 2018].

Altogether, altered inhibitory/excitatory networks in ASD-Phen1 and potential impact of STP1 could be evaluated using electrophysiology as a target engagement biomarker, but also the findings may be predictive of clinical/behavioral responses relevant to STP1 drug development.

- Lactate to pyruvate ratio (L:P)

Mitochondrial dysfunctions could explain, at least in part, the energy metabolism dysfunction observed in the ASD-Phen1 subpopulation (as described in Section 1.2.1 and 1.3.1). Whole blood lactate and pyruvate levels combined with the L:P is used to assess mitochondrial function. An elevated L:P ratio (>20) may indicate inherited

disorders of the respiratory chain complex, tricarboxylic acid cycle disorders and pyruvate carboxylase deficiency. An L:P ratio below 10 (disproportionately elevated pyruvic acid) may indicate an inherited disorder of pyruvate metabolism, such as defects of the pyruvate dehydrogenase complex. Exploratory analysis of these parameters should help understanding whether the energy metabolism impairment observed is linked to mitochondrial activity defect.

3.3 OUTCOME MEASURES

3.3.1 SAFETY OUTCOME MEASURES

The safety outcome measures for this study are as follows:

- Incidence, nature and severity of AEs.
- Incidence, nature and severity of SAEs.
- Incidence, nature and severity of AESIs.
- Incidence, nature and severity of AEs leading to treatment discontinuations.
- Changes from baseline in systolic blood pressure (SBP), diastolic blood pressure (DBP), heart rate (HR) and respiratory rate.
- Changes from baseline in orthostatic measurements of BP and HR.
- Changes from baseline in ECG parameters (HR, PQ, QRS, QT, RR and QTcF, along with information on T and U waves).
- Incidence of clinically significant ECG abnormalities.
- Hearing assessment
- Incidence of clinically relevant laboratory abnormalities, based on hematology, blood chemistry and urinalysis test results:
 - Hematology: hemoglobin, hematocrit, erythrocytes, platelet count, leucocytes differential (absolute) counts (neutrophils, eosinophils, lymphocytes, monocytes, basophils).
 - Blood chemistry: aspartate aminotransferase (AST), alanine aminotransferase (ALT), gamma-glutamyltransferase (GGT), total and conjugated bilirubin, alkaline phosphatase (ALP), albumin, creatine phosphokinase (CPK), creatinine, urea, total protein, total cholesterol, triglycerides, sodium, chloride, calcium, magnesium, phosphate, potassium, glucose.
- Incidence of value outside of the normal ranges of blood chemistry test results for electrolytes:
 - Sodium, chloride, calcium, magnesium, phosphate, potassium
- Urinalysis: protein, blood, glucose, leucocytes, nitrites, pH, and presence of crystals.

3.3.2 PHARMACOKINETIC OUTCOME MEASURES

Plasma concentrations of [REDACTED] will be used and a non-compartmental analysis (NCA) will be applied to analyze data from the sampling

schema. Urine concentration of [REDACTED] will be determined over a given period.

Plasma PK parameters such as $AUC_{0-\tau}$, AUC_{ast} , C_{\max} , T_{\max} , C_{trough} , apparent oral clearance, apparent volume of distribution and accumulation ratio will be calculated at steady state for both parent drugs. If data permitted, the elimination half-life at steady state will be estimated.

3.3.3 EXPLORATORY OUTCOME MEASURES

- Cognition, as assessed by subtasks [REDACTED] and the KiTAP battery test.
- Global clinical change in the context of autism as measured by the change in the OACIS scale.
- Maladaptive behavior, as assessed by the ABC-C.
- Change from baseline in the CGI-S scale (reflected by the CGI-I scale).
- Quality of sleep as assessed by the CSHQ.
- Electrophysiology parameters as measured by EEG at rest and during habituation and chirp tasks.
- Eye tracking.
- Change from baseline in blood L:P.

4. MATERIALS AND METHODS

4.1 CENTER

This is a single-center study to be conducted in the U.S. An additional site(s) may be included for back-up purposes and may be activated if needed.

Administrative and Contact Information and List of investigators are provided separately.

4.2 STUDY POPULATION

This study will include male and female individuals between 18 to 40 years of age (inclusive) with ASD-Phen1.

4.2.1 RECRUITMENT PROCEDURES

An observational study [[Study STP1-C003, NCT04273087](#)] is currently ongoing at Cincinnati Children's Hospital Medical Center. This study allows early identification of adult patients with ASD-Phen1 who could be potential patients in this clinical trial. However, participation in this observational study [[Study STP1-C003](#)] does not guarantee or mandate participation in this treatment protocol [[Study STP1-C004](#)].

A total of up to approximately 20 patients will be enrolled with the objective to obtain a maximum of 16 patients completing the 2-week treatment duration. The number of patients may be increased if the actual dropout rate is higher than expected, to obtain up to 16 evaluable patients. Patients must meet all the inclusion criteria and none of the exclusion criteria in order to qualify for the study, as described in [Section 4.2.2 and Section 4.2.3](#). Unless otherwise stated, inclusion and exclusion criteria refer to screening. Under no circumstances are individuals permitted to be re-randomized to receive a second course of treatment within the same cohort.

Subjects will be identified for potential recruitment per site-specific recruitment plans prior to consenting to take place on the study. Any recruitment materials for subjects and their families, will receive institutional review board (IRB) approval prior to use.

4.2.2 INCLUSION CRITERIA

Study patients must meet the following criteria for study entry:

1. Male or female (from 18 to 40 years old) individuals previously diagnosed with ASD (based on DSM-5 criteria as confirmed by the principal investigator [PI] or supported by either Autism Diagnostic Interview – Revised [ADI-R] or Autism Diagnostic Observation Schedule – Second Edition [ADOS-2] scores).
2. Patients must have a documented [REDACTED] (according to the Centers for Disease Control and Prevention [CDC] growth charts, [[CDC, 2019](#)]) or being diagnosed [REDACTED].
3. Patients with systematic aggravation of ASD behavioral symptoms occurring [REDACTED] as determined by the ASD-Phen1 semi-structured interview form.
4. Patients must have a parent or reliable caregiver who agrees to provide information about the patient as required by the protocol.
5. The patients and caregivers should be fluent in English.

6. Patient willing and consenting or assenting to participate.
7. If assent provided by the patient, parent or legal guardian willing to give written consent.
8. Patients with ASD and comorbid seizure disorder should be seizure-free for at least 6 months prior to screening.
9. Before enrolling in the study, subjects must agree to use double-barrier birth control methods if they engage in intercourse.
10. Women of childbearing potential, defined as all women physiologically capable of becoming pregnant, can be enrolled if they are using highly effective methods of contraception during dosing and for 1 week after discontinuation of the investigational drug. Highly effective contraception methods include:
 - Female sterilization (have had surgical bilateral oophorectomy with or without hysterectomy), total hysterectomy or tubal ligation at least 6 weeks before taking the investigational drug. In case of oophorectomy alone, only when the reproductive status of the woman has been confirmed by follow up hormone level assessment.
 - Male sterilization (at least 6 months prior to screening). For female patients on the study the vasectomized male partner should be the sole partner for that patient.
 - Use of oral (estrogen and progesterone), injected or implanted hormonal methods of contraception or placement of an intrauterine device (IUD) or intrauterine system (IUS) or other forms of hormonal contraception that have comparable efficacy (failure <1%), for example hormone vaginal ring or transdermal hormone contraception. Progesterone containing hormonal tablets must be associated with inhibition of ovulation in order to qualify as highly effective.
 - In case of use of oral contraception women should have been stable on the same pill for a minimum of 3 months before taking the investigational drug. If local regulations deviate from the contraception methods listed above and require more extensive measures to prevent pregnancy, local regulations apply and will be described in the informed consent form (ICF).

Women are considered post-menopausal and not of childbearing potential if they have had 12 months of natural (spontaneous) amenorrhea with an appropriate clinical profile (e.g., age appropriate, history of vasomotor symptoms) or have had surgical bilateral oophorectomy (with or without hysterectomy), total hysterectomy or tubal ligation at least 6 weeks before taking the investigational drug. In case of oophorectomy alone the reproductive status of the woman must be confirmed by follow up hormone level assessment.

Sexually active males must use a condom during intercourse after the start of the IMP administration and for at least one week after stopping study medication and should not father a child in this period after completion of the study medication. A condom is required to be used also by vasectomized men in order to prevent delivery of the drug via seminal fluid. In addition, male

participants should not donate sperm for the time period specified above.

4.2.3 EXCLUSION CRITERIA

Study patients who meet any of the following criteria will not be included in the study:

1. Patients with an identified genetic cause of ASD in their medical record will be excluded from the study.
2. History of traumatic head injury, cerebrovascular disorder, congestive heart failure, hepatic or renal disease.
3. Thrombocytopenia (platelet count <100,000 mm³) within 1 year prior to the screening visit.
4. Diabetes (type 1 diabetes mellitus or uncontrolled type 2 diabetes mellitus) or latent autoimmune diabetes of the adult (LADA).
5. Use of prohibited medications ([Section 4.5.1](#)) or herbal remedies within 2 weeks prior to randomization, or 5 half-lives (whichever is longer).
6. Alcohol and/or substance abuse/dependence within 12 months prior to screening.
7. A significant risk for suicidal behavior, in the opinion of the investigator and as assessed by the Columbia Severity Rating Scale (C-SSRS) or the simplified version adapted from the Columbia Classification Algorithm for Suicide Assessment (C-CASA).
8. Use of antioxidant supplements and/or vitamins within 2 weeks prior to randomization.
9. Initiation of, or a major change in psychological/behavioral intervention within 4 weeks prior to randomization.
10. Patient with any active infection, including but not limited to the following:
 - Bacterial infection; or
 - Fungal infection; or
 - Positive result at screening for hepatitis B virus (HBV), hepatitis C virus (HCV), or human immunodeficiency virus (HIV)-1 and severe acute respiratory syndrome coronavirus 2 (SARS-CoV-2).
11. Episode of fever (i.e., ≥100.5°F or 38.0°C) or clinically significant illness without fever (as judged by the Investigator), within 10 days before Day 1.
12. A SBP <80 mm Hg or a (DBP) <40 mm Hg or a drop in SBP of ≥20 mm Hg, or in DBP of ≥10 mm Hg, or patient experiencing lightheadedness or dizziness during the orthostatic recordings.
13. Clinically relevant ECG abnormalities; QTcF (Fredericia's correction) >450 ms (at screening or Day 1 pre-dose).
14. Confirmed clinically significant abnormal laboratory test results at screening (lactate and pyruvate not included) other than the conditions related to ASD-Phen1.
15. Patients with any active clinically significant disease (i.e. gastroenterological, endocrinological, renal, respiratory, cardiovascular, hepatic dysfunction,

immunological or hematological disease) that following the judgment of the investigator may interfere with the conduct of the study, other than the conditions related to ASD-Phen1.

16. Patients with any history of malignancy of any organ system (other than localized basal cell carcinoma of the skin), treated or untreated, within the past 5 years, regardless of whether there is evidence of local recurrence or metastases.
17. Pregnant (confirmed by laboratory testing) or lactating female patient.
18. Participation in an investigational drug study within 30 days or 5 times its half-life, whichever longer, prior to randomization.

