	
• One group will receive [REDACTED] mg twice a day (6 hours apart) oral [REDACTED] and [REDACTED] mg twice a day (6 hours apart) oral [REDACTED] (STP1 dose 1, N=6).• One group will receive matching oral placebo twice a day (6 hours apart) (N=2). 
Once first dose cohort (8 patients) finish 2 weeks of STP1 treatment and 2 weeks of follow up, a Data Safety Monitoring Board (DSMB) will evaluate the safety and tolerability data to decide whether the dose of ibudilast can be increased to 10 mg twice a day (6 hours apart) as planned, or the protocol should be modified or the study should be stopped.
 
If the DSMB supports the start of the next dose level, up to 8 additional eligible patients will be assigned to the next dose level (patients that participated in the first cohort may be allowed to participate in the second part if no safety concern was identified):
 
• [REDACTED] mg twice a day (6 hours apart) oral [REDACTED] (STP1 dose 2, N=up to 6).• One group will receive matching oral placebo twice a day (6 hours apart) (N=up to 2). 
The two drugs will be taken at the same time with food and water, and the two daily doses will be separated by approximately 6 hours. For all subjects, twice daily dosing will occur on Days 1 to 13, inclusive, and a final single dose administration will occur on the morning of Day 14 (morning dose only). On Days 1, 7 and 14, the morning dose will be taken on site.
 
The screening period is considered to be between Day -14 and Day -1. The screening visit will include the following: written informed consent, updated medical history, physical examination, drugs of abuse, pregnancy test (females only), alcohol test, laboratory safety, coagulation, viral serology, urinalysis, and inclusion/exclusion criteria. Subjects will return to the study site at scheduled visits on Day 1, Day 7 Day 14/15 and, optionally, daily up to Day 18 for evaluation and pharmacokinetic sampling, and at approximately 14 days (Day 28) after the last dose for a post-treatment safety follow-up visit.

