A battery of safety pharmacology studies that included an in vitro human ether-a-go-go-related gene (hERG) assay with ibudilast, CNS and respiratory assessments in rats and cardiovascular assessments in telemetered dogs with STP1. There were no findings that were considered adverse, as the findings were either transient, of modest magnitude, within normal ranges or of unlikely clinical significance at the doses evaluated. In addition, all the findings were readily monitorable in the clinical setting. The key findings are summarized below:

- █████ did not inhibit the hERG channel current at clinically relevant concentrations.
- In a CNS study in rats, a single oral dose of STP1 resulted in a transient and dose dependent reduction in locomotor activity (>10:1 mg/kg ibudilast/bumetanide) and body temperature (>50/5 mg/kg ibudilast/bumetanide).
- In a respiratory study in rats, a single oral dose of STP1 resulted in higher respiratory rates, with minimal changes to tidal volume, resulting in higher minute volume. These changes occurred primarily at achieved STP1 dose levels of 50/5 and 200/20 mg/kg █████.

In a cardiovascular study in dogs, an increase in heart rate was observed following STP1 dose levels >3/0.3 mg/kg █████. Changes in diastolic pressure, mean arterial pressure, pulse pressure, PR interval and QT interval were considered to secondary to heart rate, the act of vomiting/retching or a combination of the two and not a direct effect of STP1 administration. There was no effect on heart rate-corrected QT interval, Van de Water correction formula (QTcV).

Genotoxicity studies:

Based on the long clinical experience with █████ and the full genotoxicity package that has been performed to evaluate the genotoxic potential of █████ [Studies 8400253, 8400254 and 8400255], it is concluded that STP1 is not expected to have any genotoxic potential. STP1 has not yet been evaluated for carcinogenic or for reproductive and development toxicity potential.

For further information, please refer to the STP1 Investigator's Brochure [STP1-IB].

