4.6.2 TIMING OF STUDY ASSESSMENTS (SEE APPENDIX 1)

The patients willing to participate in the study will only be included when all screening examination procedures have demonstrated that all inclusion criteria and none of the

exclusion criteria apply. The patients will be assigned a patient number within the study.

Screening (Visit 1, Day -14 to Day -1)

During the screening visit the following assessments will be performed:

- Informed consent to be obtained from the patient, parent or legal guardian .
- Eligibility criteria including all inclusion and exclusion criteria.
- Demographics .
- Medical history: including all clinically significant diseases, prior medical interventions (e.g., vaccines, surgeries) or smoking/substance use history. All medication (e.g., prescription drugs, OTC drugs, herbal/homeopathic remedies, nutritional supplements) used by the patient within 4 weeks leading up to the screening visit will be collected.
- Physical examination: a general physical examination will be performed.
- Vital signs: including temperature, HR, respiratory rate, orthostatic SBP and DBP.
- ECG-12 lead.
- Serology: HIV (specific tests HIV-1 antibody), Hepatitis B (HBsAg, HBsAb) and hepatitis C virus (HCV) antibody.
- Pregnancy test (urine) in females.
- SARS-CoV-2 test (nasal swab, saliva).
- Substance abuse history, and test urine
- Blood sampling for hematology, chemistry, and coagulation.
- Urine sampling for urinalysis.
- Alcohol (urine test).
- Suicidality assessment.
- ABC-C test.
- SRS-2 test.
- SB5 ABIQ test.
- OACIS-severity assessment.
- NIH toolbox assessment.
- KiTAP assessment.
- CSHQ assessment.
- CGI-S assessment.
- AEs
- Previous and concomitant treatments.

Treatment period

The treatment period consists of 3 visits (Days 1, 7 and 14). After screening assessments, the enrolment and treatment period will be started. Patients meeting all inclusion and none of the exclusion criteria will be enrolled.

Patients will then receive the study medication, orally, twice daily (6 hours apart) for 14 days. The patient will be closely observed during and after the administration of the study medication. The following procedures and assessments will be performed during and after the treatment: Please refer to the Schedule of Assessment ([Appendix 1](#)).

Visit 2 (Day 1)

During the Day 1 visit, defined as the first day of the study drug administration, the following assessments will be performed:

- Randomization.

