4.7.1.1 DISCONTINUATION FROM STP1

Patient must discontinue STP1 if they experience any of the following:

- Pregnancy.
- Patient unable to continue to comply with study requirements.
- Unblinding of a patient.

Patients who discontinue STP1 prematurely will be asked to return to the clinic for a follow-up visit (see [Section 4.6.2.4](#)). The primary reason for premature STP1 discontinuation should be documented on the appropriate eCRF page. Patients who discontinue STP1 prematurely may be replaced to achieve a total of 16 patients.

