11. APPENDIX 1 SCHEDULE OF ASSESSMENTS

PERIOD	SCREENING	TREATMENT PERIOD			FOLLOW-UP VISITS	
		Day 1	Day 7	Day 14	Day 15-18 ^e	Day 28
Visit Window		+/-1	+/-1	+/-1	+/-2	
Assessments						
Informed Consent	x					
Eligibility	x					
Randomization		x				
Demography	x					
Medical History	x					
Physical Examination	x	x	x	x		x
Vital Signs	x	x ^a	x	x ^a		x
Orthostatic BP	x	x ^a	x	x ^a		x
ECG-12 Lead	x	x ^a	x	x ^a		x
Hearing Assessment		x	x	x		x
Serology	x					
Pregnancy Test (urine) ^b	x					x
SARS-CoV-2 Test (nasal swab, saliva)	x					
Substance Abuse (urine test)	x	x				
Blood Chemistry	x		x	x		x
Hematology	x		x	x		x
Coagulation	x		x	x		x
Urinalysis	x		x	x		x
Alcohol (urine test)	x					
Administration of Study Medication ^c		x	x	x		
Study medication supply		x				
Drug Accountability			x	x		x ^f
Blood PK Sample ^d		x	x	x	x	
Urine PK Sample ^d		x		x		
Suicidality (C-SSRS, C-CASA)	x	x	x	x	x	x
ABC-C	x			x		x
SRS-2	x			x		
SB5 ABIQ	x					
OACIS-Severity	x			x		
OACIS-Change				x		
████████	x	x		x		x
KiTAP	x	x		x		x
Eye Tracking		x		x		x
EEG		x		x		x
CSHQ	x	x		x		x
CGI-I				x		x
CGI-S	x			x		x
Adverse Events	x	x	x	x	x	x
Previous and Concomitant Treatments	x	x	x	x	x	x

a To be performed pre-dose and between 4 and 5 hours post-dose as specified in the protocol.

b Females only.

c Patients will receive their AM and PM dose of study drug during the Day 1, Day 7 and Day 14 visits to allow for proper PK sampling.

d PK samples will be collected as described in the PK assessment section. A 5 minutes window for each timepoint is allowed

e Day 16 to Day 18 are optional

f If not done at Day 14 visit

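### The pregnancy exclusion is confirmed before the first dose on a urine test that can be 1 to 14 days old, because no pregnancy test is scheduled on Day 1

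*Protocol*

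**What the plan says.** Exclusion criterion 17 (Protocol Section 4.2.3) bars any "Pregnant (confirmed by laboratory testing) or lactating female patient". Section 4.2.1 sets the reference point for eligibility: "Unless otherwise stated, inclusion and exclusion criteria refer to screening". The Synopsis defines the window: "The screening period is considered to be between Day -14 and Day -1". Section 4.4.2 then makes the first dose on Day 1 conditional on completed pre-dose assessments and confirmed eligibility.

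The visit lists in Section 4.6.2 carry the item "Pregnancy test (urine) in females" under Screening and under Day 28, and nowhere else. Appendix 1 marks the same two visits, and SAP Section 1.2 agrees. Section 4.6.1.5 mentions a urine pregnancy test without a date but refers laboratory timing to Appendix 1. Section 4.6.2.1 adds a test for patients who are rescreened, also before Day 1.

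Section 4.7.1.1 states: "Patient must discontinue STP1 if they experience any of the following". Pregnancy is first on the list that follows, and SAP Appendix B Table 1 has a row for it. Section 5.4.3.1 instructs women to report a pregnancy at once and the investigator to discontinue study drug.

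**The concern.** For pregnancy, the Day 1 confirmation of eligibility has no new result to draw on. Criterion 13 shows that the protocol can ask for a recheck: its QTcF limit applies at screening or on Day 1 before dosing. Criterion 17 has no such wording and no Day 1 test behind it.

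This is the first human study of the combination, and Section 1.3.3 says "STP1 has not yet been evaluated for carcinogenic or for reproductive and development toxicity potential". An early pregnancy that the Screening test could not detect, or that began after it, would go unseen at first dose even when the schedule is followed exactly. Urine is already collected on Day 1 for the substance test, so the missing measurement needs no new sample.

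**Working it through.** **Inputs**
- Screening window: Day -14 to Day -1 (Synopsis; Section 3.1.1).
- First dose on Day 1; last dose on the morning of Day 14 (Section 4.4.2).
- Later pregnancy test: Day 28, window ±2 days (Section 4.6.2.3).
- Latency L from conception to a positive urine test: 10 to 14 days. This is an assumption; the documents give no figure.
- There is no Day 0, so Day -1 to Day 1 counts as 1 day.

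**Step 1: the plan's own interval.** The Synopsis puts Day 28 about 14 days after the last dose. 28 - 14 = 14 days, or 12 to 16 days with the ±2-day window. This reproduces.

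**Step 2: age A of the Screening result at first dose.** Tested on Day -14, A = 14 days. Tested on Day -1, A = 1 day.

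**Step 3: tests between the two scheduled ones.** Scheduled pregnancy tests on Days 1 to 14: none. The two tests lie 28 days apart (from Day -1) to 41 days apart (from Day -14). Over the same period urine is collected for the substance test on Day 1 and for urinalysis on Days 7 and 14.

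**Step 4: conceptions that can be missed at first dose.** The window is W = A + L as scheduled and L with a Day 1 test, so the gain is A.

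| Screening test on | W as scheduled | W with a Day 1 test | Gain | Gain as share of W |
|---|---|---|---|---|
| Day -14 | 14 + 10 to 14 + 14 = 24 to 28 days | 10 to 14 days | 14 days | 14/28 to 14/24 = 50% to 58% |
| Day -1 | 1 + 10 to 1 + 14 = 11 to 15 days | 10 to 14 days | 1 day | 1/15 to 1/11 = 7% to 9% |

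Over all screening dates, W is 11 to 28 days as scheduled. These are lengths of time, not probabilities.

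**Step 5: rescreened patients.** Section 4.6.2.1 limits the time from original screening to rescreening to 2 months but states no maximum from rescreening to Day 1. The 14-day limit in Step 2 therefore applies to patients randomized within the ordinary window.

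**Step 6: contraception in the gap.** Section 4.2.2 requires agreement to double-barrier methods before enrolment (criterion 9). Criterion 10 requires highly effective methods during dosing and for 1 week afterwards. Oral contraceptives need 3 stable months before study drug, and sterilization has its own lead-in times. Intrauterine, implanted and injected methods have no stated lead-in. The days from Screening to Day 1 are partly covered, but not explicitly for every permitted method.

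**The case against.** The strongest reply is that the exclusion contains no contradiction. Criteria refer to screening by default, criterion 17 says nothing different, and a test is done at Screening. This stands: a reader might infer that the pregnancy exclusion is never properly applied, but it is applied at its stated reference point. What remains is that Section 4.4.2 asks for eligibility to be confirmed before the first dose and the schedule supplies no current result for that step.

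A reader might also infer that the discontinuation rule cannot operate and that a Day 1 test would repair it. Neither follows. Self-report (Section 5.4.3.1) and extra sampling at the investigator's discretion when symptoms call for it (Section 4.6.1.5) can both trigger the rule. A Day 1 test serves eligibility and adds nothing once dosing has started. For the same reason, the documents do not establish that an undetected pregnancy would be exposed to the whole course of 27 dosing occasions (13 × 2 + 1). That is a worst case in which neither route works.

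It is also fair to say that the contraception criteria are the main safeguard, that halving the window requires screening on Day -14, and that Section 1.3.3 speaks of the combination, not of each component. These points reduce the size of the concern. They do not remove the gap.

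**Conclusion.** The point holds in limited form. Following the schedule exactly, a woman can be randomized and dosed on a negative urine test 1 to 14 days old, although eligibility must be confirmed before that dose. Under the assumed latency of 10 to 14 days, a Day 1 test shortens the undetected window from 11-28 days to 10-14 days. The benefit is about 1 day if Screening is on Day -1 and about half the window if it is on Day -14. The number of women to be enrolled is not stated and will be small in a study of about 20 patients. No endpoint, population definition or statistical figure changes.

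Separately, mandatory discontinuation for pregnancy has no scheduled test on Days 1 to 14 and depends on self-report or discretionary testing. That is a matter for the sponsor to reconcile, not evidence that the rule is inoperable.

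**What to change.** Add a urine pregnancy test for females to the Day 1 column of Appendix 1, the Visit 2 list in Section 4.6.2 and the Day 1 list in SAP Section 1.2. Specify that it is done before randomization and before the first dose, so that criterion 17 can be confirmed as Section 4.4.2 requires. Use the urine taken that day for the substance test, and state that this sample is collected pre-dose, because neither the visit list nor the assessment sequence in Section 4.6.2 says so.

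The cost is one test strip per female patient, the wording changes, and an occasional screen failure on Day 1. Testing before randomization avoids leaving an ineligible patient already randomized. If a patient does withdraw between randomization and dosing, SAP Section 1.3.1 already reassigns the randomization number.

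The sponsor should also reconcile Sections 4.7.1.1 and 5.4.3.1 with Appendix 1 and state how pregnancy is meant to be identified during dosing. The Day 1 test does not settle that question.
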